4.4.1.1.2 Maximum Overall Intensity

Maximum overall intensity is derived from the daily intensities computed as described in [Section 4.4.1.1.1](#) and is calculated as the maximum of the daily intensities over the period considered.

4.4.1.1.3 Presence

Presence is derived from the maximum overall intensity on the period considered:

- None: No presence
- Grade 1, Grade 2, or Grade 3: Presence
- Missing: Missing presence

Subjects with at least one non-missing presence for a specific endpoint will be included in the analysis. Conversely, those without a non-missing presence will not be included in the analysis of the endpoint.

4.4.1.1.4 Time of Onset

Time of onset is derived from the daily intensities computed as described in [Section 4.4.1.1.1](#). It corresponds to the first day with intensity of Grade 1, Grade 2, or Grade 3.

Note: If a reaction is not continuous (i.e., reaction occurs over two separate periods of time intervened by at least one daily intensity Missing or None) then the time of onset is the first day of the first occurrence.

4.4.1.1.5 Number of Days of Occurrence

Number of days of occurrence over the period considered is derived from the daily intensities computed as described in [Section 4.4.1.1.1](#). It corresponds to the number of days with daily intensities of Grade 1, Grade 2, or Grade 3. Number of days of occurrence on the solicited period with a specified intensity may also be derived.

4.4.1.1.6 Overall Number of Days of Occurrence

If a reaction is ongoing at the end of the solicited period, then the overall number of days of occurrence is derived from the daily intensities and the stop date of the reaction after the end of the solicited period. The overall number of days of occurrence is:

- (stop date – last vaccination date) + (number of days of occurrence within the solicited period) – length of the solicited period + 1

If the stop date is missing or incomplete (contains MD), the overall number of days of occurrence will be considered as Missing.

4.4.1.1.7 Ongoing

Ongoing is derived from the last daily intensity of the solicited period computed as described in Section 4.4.1.1.1 and the maximum intensity on the ongoing period. The investigator's ongoing flag is not used because the measurement would determine the ongoing status of the reaction. If the last daily intensity of the solicited period is at least Grade 1 and maximum intensity on the ongoing period is also at least Grade 1, then the reaction is considered ongoing. In any other cases the reaction will not be considered as ongoing.

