### 9.3.2.3.2 Reactogenicity (Solicited Reactions from D0 to D07 after Vaccination)

After vaccination, subject's parent/legally acceptable representative will be provided with a safety diary card, a digital thermometer, and a flexible ruler, and will be instructed how to use them. The following items will be recorded by the subject's parent/legally acceptable representative in the diary card on the day of vaccination and for the next 7 days (i.e., D0 to D07) until resolution:

- Daily temperature, with the route by which it was taken
- Daily measurement or intensity grade of all other solicited injection site and systemic reactions
- Action taken for each event, if any (e.g., medication)

The action taken by the subject's parent/legally acceptable representative to treat any solicited reactions will be classified in the CRF using the following scale:

- 0: None
- 1: Medication (self-medication with an existing prescription or over-the-counter medication)
- 2: Health care provider contact (no new medication prescribed)
- 3: Health care provider contact and prescription of a new medication (health care provider instructed subject to take a new medication, either an over-the-counter medication or one requiring a written prescription)
- 4: Hospitalization (inpatient)

Subject's parents/legally acceptable representatives will be contacted by telephone 8 days (+2 days) after vaccination to remind them to record all safety information in the diary card.

If the timing of the telephone call should fall on a weekend or a holiday, the call should be made on the next business day. If contact is not made on the designated day, study staff will continue calling until contact is made. Every telephone attempt and its outcome will be documented in the source document.

[Table 9.1](#) and [Table 9.2](#) present, respectively, the injection site reactions and systemic reactions that are prelisted in the diary cards and CRF, together with the intensity scales.

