4.4 Derived Endpoints: Calculation Methods

4.4.1 Safety

4.4.1.1 Solicited Reactions

4.4.1.1.1 Daily Intensity

All daily records for solicited reactions will be derived into daily intensity according to the following classification: None, Grade 1, Grade 2, Grade 3, or Missing.

For the derivation of daily intensities the following sequential steps will be applied:

- 1) Solicited reactions (except Fever) with an investigator presence recorded as “No” and with all daily records missing then all daily intensities will be derived as None.
- 2) For a temperature partially missing after decimal point, the data will be analyzed replacing “MD” (missing data) by zero. For example, a “39.MD” daily temperature will be considered as “39.0°C” at the time of analysis.
- 3) For non-measurable solicited reactions, daily intensities will correspond to daily records reported in the clinical database. For measurable solicited reactions the daily measurements reported in the clinical database will be converted based upon the intensity scales defined in the protocol; this assumes a reaction that is too large to measure (non measurable, “NM”) is Grade 3.

Note: The maximum intensity on the ongoing period is derived from the record of the maximum intensity/measurement after the end of the solicited period following the rule described above.

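### SAP 4.4.1.1.7 classes a solicited reaction as not ongoing when the D07 or post-D07 intensity is Missing, even if a later stop date or the investigator's flag shows that it continued

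*SAP*

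**What the plan says.** Protocol 9.3.2.3.2 asks parents to record solicited reactions on the day of vaccination and "for the next 7 days (i.e., D0 to D07) until resolution".

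SAP 4.4.1.1.1 derives each "daily intensity according to the following classification: None, Grade 1, Grade 2, Grade 3, or Missing". Its closing note adds: "The maximum intensity on the ongoing period is derived from the record of the maximum intensity/measurement after the end of the solicited period", by the same rule. Both inputs to the ongoing status can therefore be Missing.

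SAP 4.4.1.1.7 sets two conditions. The first reads "If the last daily intensity of the solicited period is at least Grade 1". The second reads "maximum intensity on the ongoing period is also at least Grade 1, then the reaction is considered ongoing". The default for all remaining combinations is "In any other cases the reaction will not be considered as ongoing". On the investigator's own record, the section says that the "ongoing flag is not used because the measurement would determine the ongoing status of the reaction". The stop date is not among the inputs.

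SAP 4.4.1.1.6 brings the stop date into the overall number of days only for a reaction that is ongoing at the end of the solicited period. For those reactions it adds: "If the stop date is missing or incomplete (contains MD), the overall number of days of occurrence will be considered as Missing". It gives no overall value for a reaction that is not ongoing.

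**The concern.** The default treats an unknown value as a negative answer. A child with swelling graded on D07 and a stop date of D12 on file is classed as not ongoing if the post-D07 maximum was left blank. The reason given for ignoring the flag assumes that a measurement exists; where it does not, the SAP sets aside the remaining evidence and still assigns a definite status.

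This is out of line with the SAP's handling of missing safety data elsewhere. Missing presence stays Missing (4.4.1.1.3). A missing stop date makes the overall duration Missing (4.4.1.1.6). Missing causality is taken as related (5.3.1.2), which is the cautious direction. The ongoing rule goes the other way, and only one way: a missing intensity can remove a continuing reaction from the ongoing class but can never add one.

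At stake is the part of the reactogenicity description that looks past D07, which the plan derives through these two variables.

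**Working it through.** The plan states no figure to reproduce. The check is a truth table of the rule, followed by the SAP's own duration formula.

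**Truth table** (SAP 4.4.1.1.7, with Missing allowed by 4.4.1.1.1)

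| D07 intensity | Post-D07 maximum | SAP result | What the two values support |
|---|---|---|---|
| Grade 1 or more | Grade 1 or more | ongoing | ongoing |
| Grade 1 or more | None | not ongoing | not ongoing |
| Grade 1 or more | Missing | not ongoing | undetermined |
| None | None, Grade 1 or more, or Missing (3 rows) | not ongoing | not ongoing |
| Missing | None | not ongoing | not ongoing |
| Missing | Grade 1 or more | not ongoing | undetermined |
| Missing | Missing | not ongoing | undetermined |

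Of 9 combinations, 1 is ongoing. All 5 with at least one Missing value are not ongoing. Two of those 5 are right on the recorded value; the other 3 are undetermined by the intensities, and there the stop date and flag are the only evidence left. Step 1 of SAP 4.4.1.1.1 does not help, because it sets intensities to None only when the investigator records presence as No and every daily record is missing.

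**Duration formula** (SAP 4.4.1.1.6): (stop date − vaccination date) + in-period days − length of solicited period + 1. The length is taken as 8 diary days, D0 to D07.

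Illustrative data, not from the trial:

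- *Complete record.* Swelling on D05, D06 and D07, post-D07 maximum Grade 1, stop date D12: 12 + 3 − 8 + 1 = 8 days. Counting D05 to D12 directly also gives 8, which confirms the length of 8; a length of 7 would give 9.
- *Post-D07 maximum blank, all else the same.* The reaction is classed as not ongoing, so the formula is not applied. What remains is the in-period count of 3.
- *D07 blank.* Swelling on D05 and D06, post-D07 maximum Grade 1, stop date D12. Again classed as not ongoing, leaving 2 in-period days. The formula would give 12 + 2 − 8 + 1 = 7, with the blank D07 not counted.

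**Frequency.** The documents give no rate of missing intensities and no rate of reactions lasting beyond D07. Purely as an assumption, let 2% to 10% of the 510 planned MenACYW children (306 + 204) have a continuing reaction, and let 1% to 20% of those lack one of the two intensities. At 2%, 10.2 continuing reactions would be classed as 8.2 to 10.1; at 10%, 51.0 as 40.8 to 50.5. The relative loss equals the missing fraction, and with complete data it is zero.

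**The case against.** The strongest reply is that little of what is reported depends on this rule. The protocol's solicited endpoints concern reactions up to 7 days after vaccination (Protocol 9.3.2.2), and SAP 4.4.1.1.2 to 4.4.1.1.5 derive maximum intensity, presence, onset and days of occurrence from the daily grades alone. Safety is descriptive, with no hypotheses. The rule is the same for both vaccines. Diary review at V02, clarification of incomplete entries and data queries (Protocol 5.1.4, 11.1, 11.2) should make blanks uncommon. All of this stands, and it sets the size of the point. It does not make the rule right where a blank remains.

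The D07-blank example also depends on reading the last daily intensity as that of D07. If it means the last non-missing day, that example disappears. The SAP does not say which is meant. The example with D07 graded and the post-D07 maximum blank stands either way.

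A reader might infer more, and the documents do not support it:

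- *That a reported count of persistent reactions is too low.* SAP 5.1.3.2 names onset, days of occurrence and action taken among its summaries. It does not promise a table of reactions lasting beyond D07.
- *That the SAP reports 3 days where 8 is true.* SAP 4.4.1.1.6 gives no overall value for a reaction that is not ongoing. The 3 is a correct D0 to D07 count, left standing by implication.
- *That such cases are routine.* No frequency is given. A family that stops responding after D07 would usually leave D07 blank too, since the card is collected at V02.
- *That the vaccine comparison is distorted.* That would need missingness to differ between groups, and nothing in the documents points to it.
- *That a reaction recorded as None on D07 with a later stop date is also misclassified.* Protocol 9.3.2.1 treats an event that starts on D08 as unsolicited. A return after a recorded None is a recurrence or a new event, so not ongoing is correct.

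**Conclusion.** The point holds in a narrow form. As written, SAP 4.4.1.1.7 gives a definite negative when an intensity it needs is Missing, and does so even where a later stop date or the investigator's flag shows that the reaction continued. The error runs in one direction and is confined to the ongoing status and, by implication, the overall number of days of occurrence; in the worked case 8 days would be available and only the 3 in-period days remain. The size in this trial cannot be worked out, because it depends on how complete the D07 and post-D07 entries are. The conclusion rests on taking the default sentence literally and on a solicited period of 8 days. It is worth correcting before analysis because the change is small, but it bears on no primary or secondary result.

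**What to change.** Amend SAP 4.4.1.1.7, with a matching sentence in 4.4.1.1.6:

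- Both intensities recorded: keep the current rule.
- D07 at least Grade 1 and post-D07 maximum Missing: ongoing if the stop date is after D07 or, with no stop date, if the investigator's flag is Yes. If neither is available, set ongoing status and overall number of days to Missing. Where the flag alone decides, the existing missing-stop-date rule already makes the overall days Missing.
- D07 Missing, with a post-D07 maximum of at least Grade 1 or a stop date after D07: set ongoing status and overall days to Missing, unless the flag confirms continuation.
- D07 recorded as None: not ongoing, whatever follows.

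State whether the last daily intensity means D07 or the last non-missing day, and what overall number of days a reaction classed as not ongoing receives. Report, by group, how many reactions had their status settled by the stop date or flag, and how many were set to Missing.

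The cost is a few sentences and a small change to the derivation program. The downside is that a few more durations will be reported as longer or as Missing.

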4.4.1.2 Unsolicited Non-serious AEs

4.4.1.2.1 Presence

An observation will be considered an event if it has at least a verbatim term and is not a Grade 0 intensity event. Grade 0 events should be included in the listing "Unsolicited non-serious adverse events not included in the safety analysis."

4.4.1.2.2 Intensity

Intensity for unsolicited non-serious adverse event (AE) will be derived according to the following classification: None, Grade 1, Grade 2, Grade 3, or Missing.

If the unsolicited non-serious AE is measurable and its preferred term is part of the list of solicited reactions, then the measurement is derived based upon and following the same rule than the intensity scales defined in the protocol for that measurable injection site or systemic reaction.

Intensity for the other unsolicited non-serious AEs will correspond to the value reported in the CRF.

The maximum intensity corresponds to the highest intensity for a unique term.

4.4.1.2.3 Last Vaccination

Last vaccination before an unsolicited non-serious AE is derived from the visit numbers provided in the clinical database and is calculated as follows:

- If an unsolicited non-serious AE has a non-missing visit number, the visit number should be used to determine the last vaccination before the unsolicited non-serious AE

If the visit number is missing, then the start date should be used to determine the last vaccination before the unsolicited non-serious AE

4.4.1.2.4 Time of Onset

Time of onset is derived from the start date of the unsolicited non-serious AE provided in the clinical database and the date of last vaccination:

- start date of the unsolicited non-serious AE – date of previous vaccination

The time of onset should be considered as missing only if one or both of the dates are missing or partially missing.

The unsolicited non-serious AEs will be analyzed “Within 30 days”, which corresponds to AEs with a time of onset between 0 and 30 days after vaccination or missing. An AE with missing time of onset will be considered to have occurred just after the vaccination indicated by the visit number, so will be included in these tables.

Note: Unsolicited non-serious AE that occurred before vaccination (negative time of onset) or with a time of onset higher than defined above will not be included in analysis, but will be listed separately.

4.4.1.2.5 Duration

Duration is derived from the start and stop dates of the unsolicited non-serious AE provided in the clinical database:

- stop date of unsolicited non-serious AE - start date of unsolicited non-serious AE + 1.

The duration should be considered as missing only if one or both of the start and stop dates of the unsolicited non-serious AE is missing or partially missing.

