**9.3.2.3.3 Unsolicited Non-serious Adverse Events from D0 to Day 30 after Vaccination**

In addition to recording solicited reactions, parents/legally acceptable representatives will be instructed to record any other medical events that may occur during the 30 day period after vaccination. Space will be provided in the diary card for this purpose.

For each unsolicited non-serious AE, the following information is to be recorded:

- Start and stop datesa
- Intensity of the event:
  - For measurable unsolicited non-serious AEs that are part of the list of solicited reactions, the size of the AE as well as the temperature for fever will be collected and analyzed based on the corresponding scale used for solicited reactions (see [Table 9.1](#) and [Table 9.2](#))
  - Other unsolicited non-serious AEs will be classified according to the following intensity scale:
    - Grade 1: No interference with activity
    - Grade 2: Some interference with activity
    - Grade 3: Significant; prevents daily activity
- Action taken for each AE, if any (e.g., medication)

The action taken by the parent/legally acceptable representative to treat any **unsolicited AEs** will be classified in the CRF using the following scale:

0: None

1: Medication (self-medication with an existing prescription or over-the-counter medication)

2: Health care provider contact (no new medication prescribed)

---

a The stop date of all related AEs will be actively solicited. For other events, the investigator will provide the stop date when it becomes available. AEs for which no stop date was obtained during the course of the trial will be considered as ongoing at the end of the trial.

3: Health care provider contact and prescription of a new medication (health care provider instructed subject to take a new medication, either an over-the-counter medication or one requiring a written prescription)

- Whether the AE led to discontinuation
- Whether the AE was related to vaccination (for unsolicited systemic AEs)

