4.4.1.3.3 Duration

Duration will be computed using the same methodology as for unsolicited non-serious AEs described in [Section 4.4.1.2.5](#).

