5.3.1.5 Start Date and Stop Date

Missing or partially missing start dates for unsolicited AEs will remain missing and not be imputed. If either the start or stop date is missing or partially missing, the time of onset will be considered to be missing. Nevertheless unsolicited AEs with missing time of onset will be included in analyses according to the visit collected.

Missing or partially missing stop dates for AEs (solicited reactions and unsolicited AEs) will remain missing and not be imputed.

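### Unsolicited AEs and SAEs with no stop date get a missing duration in the SAP, although the protocol calls such AEs ongoing; the duration summary mixes persisting events with lost dates and leans short.

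*SAP*

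**What the plan says.** **Endpoint.** Protocol 9.3.2.2 lists duration for immediate unsolicited systemic AEs, unsolicited AEs and SAEs. SAP 5.1.3.2 tabulates unsolicited AEs by the categories named in the endpoints.

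**SAP rule.** Section 4.4.1.2.5 defines duration as "stop date of unsolicited non-serious AE - start date of unsolicited non-serious AE + 1". Its rule for absent or incomplete dates begins "The duration should be considered as missing only if one or both of the start and stop dates", and it covers partial as well as wholly absent dates. For SAEs, 4.4.1.3.3 states: "Duration will be computed using the same methodology as for unsolicited non-serious AEs". Section 5.3.1.5 says that missing or partial AE stop dates "will remain missing and not be imputed".

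**Protocol status of the same records.** Footnote a in 9.3.2.3.3 reads: "AEs for which no stop date was obtained during the course of the trial will be considered as ongoing at the end of the trial". The same footnote says that stop dates of related AEs are actively sought, and that for other events the investigator supplies the date once it is available.

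**Ongoing in the SAP.** Only 4.4.1.1.7 derives an ongoing status, and it covers solicited reactions. Unsolicited AEs and SAEs have no ongoing category and no minimum duration.

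**The concern.** An event usually lacks a stop date because it has not ended. The missingness therefore depends on the quantity being summarised, and longer events are more likely to lose their duration. Follow-up lasts only 30 to 44 days, and AEs with onset up to Day 30 are analysed, so a late event has little time to resolve on study.

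The protocol already gives these records a meaning. Once the SAP codes them as missing, a persisting event looks the same as one whose date was never written down. What is at stake is how well a descriptive endpoint can be read: persistent events would be under-represented in the duration categories for both vaccines.

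**Working it through.** The documents give no figure for this point, so there is none to reproduce.

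**1. What is known about an ongoing event.** Take onset on Day 25, still present at Visit 2 (Day 30 to Day 44). By the SAP formula its duration is at least 30 − 25 + 1 = 6 days, and up to 44 − 25 + 1 = 20 days if Visit 2 is late. Under 4.4.1.2.5 it is missing. If no later stop date is used, the longest duration that can be computed is 44 − 0 + 1 = 45 days.

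**2. Share of durations lost.** Inputs from the documents: onset window Day 0 to 30 (SAP 4.4.1.2.4) and Visit 2 at Day 30 to 44 (protocol Table of Study Procedures). Assumptions not in the documents: onset and Visit 2 uniform over those windows, exponential durations with mean m, and no stop date after Visit 2 used. The time from onset to Visit 2 is then the sum of a uniform on (0, 30) and a uniform on (0, 14), so

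share lost = (m/30)(1 − e^(−30/m)) × (m/14)(1 − e^(−14/m)).

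- m = 5: 0.1663 × 0.3354 = 0.056
- m = 10: 0.3167 × 0.5381 = 0.170
- m = 14: 0.4119 × 0.6321 = 0.260

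With dates simulated as whole days, the shares are 5.1% (m = 5) and 15.9% (m = 10). Log-normal durations (log SD 1) give 5.3% and 14.5%.

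**3. Which durations are lost.** In the whole-day simulations with both distributions, 28% to 32% of the longest tenth of events lose their duration at mean 5 days, and 75% at mean 10. Only 2% to 4% of the lost durations are shorter than the true median.

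**4. Effect on a duration category.** The documents set no duration cut, so 8 days is only an example. With calendar days and the +1, the true share lasting 8 days or more is m(e^(−6/m) − e^(−7/m)). The share counted under the SAP rule is simulated.

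| Assumed mean (days) | True share ≥ 8 days | Counted, all events as denominator | Undercount | Share among non-missing |
|---|---|---|---|---|
| 5 | 0.273 | 0.226 | about 17% | 0.239 |
| 10 | 0.522 | 0.358 | about 31% | 0.432 |
| 14 | 0.629 | 0.374 | about 40% | 0.505 |

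If percentages are taken among non-missing durations, the relative shortfall is smaller: 1 − 0.239/0.273 = 12%, 1 − 0.432/0.522 = 17% and 1 − 0.505/0.629 = 20%. The SAP does not say which denominator applies.

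**The case against.** **The plan contains no statistic that is clearly harmed.** SAP Table 5.1 lists clinical safety results as categorical only, with no mean or median duration and no stated duration categories. This stands: figures for a distorted mean would describe outputs that are not planned. Duration is still an endpoint to be tabulated, and categories are biased in the same direction.

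**The two documents do not contradict each other.** One assigns a status and the other declines to invent a date. A reader might infer a conflict, but both rules can be followed together. The gap is that the SAP does not carry the status into its derivations.

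**Much of the loss is already prevented.** Protocol 5.1.4 and 9.3.2.3.6 follow unresolved related AEs and SAEs after the trial, and 10.2 requires SAE forms to be updated. SAE outcome is summarised separately (SAP 4.4.1.4.4), and stop dates for other AEs are entered when available. This stands and makes the calculation above an upper figure for followed events. It is not complete protection: follow-up may end when a condition is stable or chronic, and the documents do not say whether dates obtained after the trial enter the analysis database.

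**Some blanks are administrative.** A short early illness with an unrecorded end would be given a duration of about 30 days or more if minimum durations were merged with completed ones. If 5% or 10% of resolved events lacked a date (assumed), merging would overcount events of 8 days or more by roughly 8% or 20% at mean 5 days. Merging also sits badly with the no-replacement rule for safety data in both documents. This stands, and it determines the form of the fix.

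**Conclusion.** The point holds as a limited reporting defect. The SAP rule removes persisting events from the duration summary, does not distinguish them from lost dates, and biases what remains toward short events, mainly among AEs judged unrelated. About 6% to 26% of durations would be lost at assumed means of 5 to 14 days. That range rests on uniform timing, exponential durations and no use of stop dates after Visit 2, none of which the documents establish.

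A reader might infer more, and the documents do not support it:

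- **Events vanish from the safety analysis.** They do not; they stay in the incidence, intensity and relatedness tables.
- **The rule favours one vaccine.** It is the same for both, and nothing in the documents points to a differential effect.
- **Trial conclusions are at risk.** Safety is descriptive with no hypothesis, and the primary and secondary objectives are immunogenicity only.
- **SAEs are hit as hard as other AEs.** The SAP rule reaches them, but the protocol footnote sits in the non-serious section, and SAE follow-up and outcome reporting soften the loss.

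**What to change.** In SAP 4.4.1.2.5 and 4.4.1.3.3, class an event with a known start date and no stop date as *ongoing at end of trial*. Show it as its own row in the duration tables. Keep *missing* for an unknown start date or a partial stop date. Give the minimum duration (last contact − start + 1) in the listing or as a sensitivity count, without merging it with completed durations. No stop date is imputed, so 5.3.1.5 can stay as it is, and no survival-type estimate is needed. It would also help to state whether stop dates obtained after Visit 2 are used.

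Cost: a sentence in each of two sections and one table row, from data already collected. The downside is that some administratively blank stop dates will be shown as ongoing, which the protocol footnote already does.
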